| 16.6 Monitoring | 32 |
| 16.7 Subject Confidentiality..... | 32 |
| 17 ADMINISTRATIVE, ETHICAL, REGULATORY CONSIDERATIONS | 32 |
| 17.1 Protocol Amendments..... | 32 |
| 17.2 Institutional Review Boards and Independent Ethics Committees | 32 |
| 17.3 Informed Consent Form | 33 |
| 17.4 Publications..... | 33 |
| 17.5 Investigator Responsibilities | 34 |

LIST OF ABBREVIATIONS

| | |
|---------------|---|
| AE | Adverse event |
| CC | Cubic Centimeter |
| CFR | Code of Federal Regulations |
| CRF | Case report form |
| CT | Computed Tomography |
| DMC | Data Monitoring Committee |
| FDA | Food and Drug Administration |
| GCP | Good Clinical Practice |
| HIPAA | Health Insurance Portability and Accountability Act of 1996 |
| IV | Intravenous Administration |
| ICF | Informed consent form |
| ICH | International Conference on Harmonisation |
| IEC | Independent Ethics Committee |
| IRB | Institutional Review Board |
| KG | Kilogram |
| MG | Milligrams |
| MRI | Magnetic Resonance Imaging |
| PET-CT | Positron Emission Tomography-Computed Tomography |
| PI | Principal Investigator |
| PO | Oral Administration |
| SAE | Serious adverse experience |

PROTOCOL SYNOPSIS

| | |
|-----------------------------------|--|
| TITLE | Minimally Invasive Thoracic Surgery Intercostal Nerve Block Trial |
| SPONSOR | Sponsor-Investigator |
| FUNDING ORGANIZATION | Internal – UCSF Department of Surgery, Division of Cardiothoracic Surgery |
| NUMBER OF SITES | 1 |
| RATIONALE | Subjects who undergo minimally invasive lung surgery have postoperative surgical pain. Uncontrolled surgical pain of the chest wall can result in splinting, atelectasis, and pneumonia. The optimal strategy to manage surgical pain from minimally invasive thoracic surgery is unknown. With the development of Liposomal Bupivacaine, a sustained-release formulation of Standard Bupivacaine, there has been renewed interest in regional intercostal nerve blockade. While Standard Bupivacaine loses efficacy after 8 hours, Liposomal Bupivacaine has the potential efficacy of 96 hours. The trial data supporting Liposomal Bupivacaine were performed outside of thoracic surgery in local wound infiltration (not regional nerve blockage), and the data within thoracic surgery are limited and based upon observational studies. |
| STUDY DESIGN | Randomized, double-blind, active-comparator controlled clinical trial |
| PRIMARY OBJECTIVE | To assess the analgesic efficacy of intraoperative intercostal nerve block and wound infiltration by Liposomal Bupivacaine versus Standard Bupivacaine in subjects undergoing minimally invasive lung resection. |
| SECONDARY OBJECTIVES | To assess if there are changes in perioperative outcomes in intercostal nerve block by Standard Bupivacaine versus Liposomal Bupivacaine: pulmonary complications, length of stay, direct hospital costs, quality of life. |
| NUMBER OF SUBJECTS | 80 |
| SUBJECT SELECTION CRITERIA | 
Inclusion Criteria:
 
 - Robotic or video-assisted lung resection for all indications - Surgeons: [name] MD, [name] MD, [name] MD 
Exclusion Criteria:
 
 - Additional thoracic procedures and/or extra-thoracic procedures - Reported hypersensitivity to amide local analgesia - Cardiac Conduction Abnormalities |

| | |
|--|--|
| | 
 - Hepatic Dysfunction - Renal Dysfunction - Preoperative Neuropathic Pain requiring tricyclic antidepressants or calcium channel alpha 2-delta ligands - Preoperative Daily Opioid Usage - <18 years of age |
| TEST PRODUCT, DOSE, AND ROUTE OF ADMINISTRATION | 
Liposomal Bupivacaine
 
 - 5cc of drug preparation will be percutaneously injected into each intercostal space 3-10 under direct intrathoracic vision and subcutaneously into each surgical wound at the conclusion of the surgery. |
| CONTROL PRODUCT, DOSE AND ROUTE OF ADMINISTRATION | 
Standard Bupivacaine
 
 - 5cc of drug preparation will be percutaneously injected into each intercostal space 3-10 under direct intrathoracic vision and subcutaneously into each surgical wound at the conclusion of the surgery. |
| DURATION OF SUBJECT PARTICIPATION AND DURATION OF STUDY | 
Subjects will be on study for up to 30 days following their surgery.
 
Screening: Preoperative Clinic Visit
 
Treatment: Conclusion of surgery (all subjects admitted to the hospital for standard postoperative care)
 
Follow Up: Postoperative Clinic Visit
 
The total duration of the study is expected to be 8 months.
 |
| CONCOMMITANT MEDICATIONS | 
Allowed:
 
Standardized Hospital Pain Medication Regimen
 
All subjects will receive a standardized postoperative pain regimen. Goal pain management is to allow the subject to ambulate and perform incentive spirometry per standard care. Escalation of opioid dosing if needed will be at the discretion of the inpatient surgery team.
 
Standardized Discharge Pain Medication Regimen
 
All subjects to be discharged on a standardized pain regimen.
 
Prohibited:
 
None
 |
| EFFICACY EVALUATIONS | |
| PRIMARY ENDPOINT | 
 • Cumulative Daily In-Hospital Use of Opioids (morphine equivalents in mg) |
| SECONDARY ENDPOINTS | 
 • Cumulative Daily In-Hospital Pain Score (0-10) • Mean Time to First Opioid Use (hours) |

| | |
|---|---|
| | 
 • Mean Time to Ambulation (hours) • Pulmonary Complications (y/n) • Liposomal & Standard Bupivacaine Adverse Events (y/n) • Total Opioid Prescription at Discharge (morphine equivalents in mg) • Total Opioid Use as Outpatient (morphine equivalents in mg) • Length of Stay (days) • Direct Costs of Hospital Encounter (dollars) • Quality of Life: Short-Form-8 Health Survey |
| OTHER EVALUATIONS | n/a |
| SAFETY EVALUATIONS | 
 - All subjects will be monitored with continuous cardiac telemetry throughout the entirety of their hospitalization. - Nursing staff will assess the mental status of each participant at the start of each shift. - Surgical wounds will be monitored daily by the surgery inpatient team. - The minimum duration of inpatient monitoring is 24 hours. For subjects that are discharged on POD1 after 24 hours of monitoring, a safety assessment will be performed on POD2. - Adverse events will be assessed continuously, starting with the first patient enrollment and until study completion, and will be immediately reported to the Medical Monitor. - Serious and severe adverse events, regardless of causality, will be followed until resolution or stabilization. - Subjects will be discharged with specialized discharge instructions to alert them of potential adverse effects and instruct them when to call the clinic. |
| PLANNED INTERIM ANALYSES | When the study has reached 1/3 and 2/3 goal enrollment, interim analysis for safety will be conducted by an independent data monitoring committee. Serious and severe adverse events will be monitored by the committee on an ongoing basis throughout the study. |
| STATISTICS Primary Analysis Plan & Rationale | 
Null Hypothesis: There is no difference in cumulative daily in-hospital use of opioids in subjects who receive intercostal nerve block and wound infiltration with Liposomal Bupivacaine or Standard Bupivacaine during minimally invasive lung resection.
 
Statistical Method: Student's t-test.
 
Rationale: 80 subjects will provide 80% power to detect a statistically significant effect with 2-sided alpha error set at 0.05 if the measured effect is 19% absolute reduction in cumulative daily in-hospital use of opioids.
 |

| | |
|--|---|
| | 
The mean cumulative daily in-hospital usage of opioids is 35mg morphine equivalents with standard deviation of 12mg. This was estimated by review of previously published studies and corroboration with UCSF clinical practice patterns. A 19% reduction in cumulative daily in-hospital use of opioids corresponds to 1 fewer oxycodone dose per day, which was considered clinically significant.
 |
|--|---|

1 BACKGROUND

In the study, subjects undergoing minimally invasive lung surgery will receive a one-time intraoperative intercostal nerve block and wound infiltration with Standard Bupivacaine or Liposomal Bupivacaine.

Standard Bupivacaine

Standard Bupivacaine (*Marcaine*[®]; Hospira Inc; Lake Forest, IL) is an amide local anesthetic that is commonly used in the operating room for wound infiltration and regional nerve block. Onset of action is 5-10 minutes and duration is up to 8 hours [1].

Liposomal Bupivacaine

Liposomal Bupivacaine (*Exparel*[®]; Pacira Pharmaceuticals Inc; Parsippany, NJ) is a sustained-release formulation of Standard Bupivacaine [2]. Onset of action is within 10 minutes and duration is up to 96 hours [3]. Liposomal Bupivacaine is FDA-approved for single-dose infiltration into the surgical site to produce postsurgical analgesia since 2015 and brachial plexus regional nerve block since 2018. In clinical practice and research, it is also being used off-label for other forms of regional nerve block (including intercostal nerve block). Liposomal Bupivacaine is being used at UCSF for all procedures associated with an enhanced recovery program, which includes thoracic surgery.

1.1 Overview of Non-Clinical Studies

Liposomal Bupivacaine is a novel formulation of Standard Bupivacaine that is designed to provide sustained-release. Multivesicular liposomes release Standard Bupivacaine over an extended period of time due to diffusion, lipid membrane erosion, and lipid membrane reorganization [4]. 266mg Liposomal Bupivacaine (planned dose for the study) reaches peak plasma levels at 12 hours and levels can be detected up to 96 hours after administration. About 3% of the Liposomal Bupivacaine formulation contains extra-liposomal Standard Bupivacaine to provide immediate analgesic coverage until there is adequate liposomal release [3]. The active component Standard Bupivacaine is an amide local anesthetic that binds the voltage-gated sodium channels of the neuron and inhibits conduction of pain. Standard Bupivacaine is metabolized in the liver by cytochrome P450 and excreted by the kidneys [5]. The remnant liposomes and lipid membranes slowly degrade and are eliminated through systemic absorption [4].

1.2 Overview of Clinical Studies

Liposomal Bupivacaine has been studied in a variety of surgical specialties in both wound infiltration and regional nerve block. Comparison of studies is limited by different surgical procedures, placebo versus active control, and varied primary and secondary outcomes.

The initial trials of Liposomal Bupivacaine were in wound infiltration [6]. In comparison to placebo, subjects undergoing hemorrhoidectomy had lower cumulative pain score and lower cumulative opioid consumption in the first 72 hours after surgery [7]. In comparison to Standard Bupivacaine, subjects undergoing breast augmentation had lower mean pain score at 12 hours and no difference for the remaining hospital stay [8]. Subsequent trials have evaluated Liposomal Bupivacaine in regional nerve block [9]. In

comparison to Standard Bupivacaine, subjects undergoing robotic-assisted hysterectomy with abdominal wall nerve block had lower cumulative opioid use in the first 72 hours after surgery and subjects undergoing shoulder arthroplasty had reduced pain scores and opioid consumption in the first 48 hours [10, 11]. The most common adverse events associated with Liposomal Bupivacaine from these studies were nausea, emesis, and/or constipation. Cardiac and neurologic toxicity were not reported [6, 9].

Liposomal Bupivacaine is FDA-approved for single-dose infiltration into the surgical site to produce postsurgical analgesia since 2015 and brachial plexus regional nerve block since 2018. In clinical practice and research, it is also being used off-label for other forms of regional nerve block (including intercostal nerve block).

In thoracic surgery, there are two published studies that were both observational and retrospective. They evaluated intercostal nerve block versus epidural analgesia in subjects undergoing lung resection by both thoracotomy and minimally invasive techniques [12, 13]. Rice et al showed that there was no difference in pain scores, opioid use, or postoperative complications between groups. However, Khalil et al showed that there were lower mean pain scores on postoperative day one and three, no difference in opioid usage, and lower pulmonary complications in subjects that received Liposomal Bupivacaine [**Error! Bookmark not defined.**]. There is also an unpublished randomized, placebo-controlled trial in subjects that underwent thoracotomy and intercostal nerve block. They did not find a difference in pain scores or total opioid consumption.

There are currently three registered clinical trials at ClinicalTrials.gov evaluating Liposomal Bupivacaine in lung resection surgery. The Mayo Clinic is performing a non-inferiority trial of epidural analgesia versus intercostal nerve block with Liposomal Bupivacaine in subjects undergoing open lung resection [14]. Inova Health Care Services is performing a trial assessing local wound infiltration with Liposomal Bupivacaine versus Standard Bupivacaine in subjects undergoing thoracoscopy [15]. Massachusetts General Hospital is performing a trial evaluating intercostal nerve block with Liposomal Bupivacaine, Standard Bupivacaine, Standard Bupivacaine with epinephrine, and normal saline in subjects undergoing video-assisted lung resection [16]. Each of these studies address questions different from this proposal. Moreover, the results from these studies are not expected within the next year.

2 STUDY RATIONALE

Subjects who undergo minimally invasive thoracic surgery have acute, postoperative surgical pain. Uncontrolled surgical pain of the chest wall can result in splinting, atelectasis, and pneumonia [17]. There are a variety of multimodality analgesic strategies currently employed in the clinical setting; however, the optimal strategy to provide analgesia while minimizing analgesic-related complications is unknown. With the development of Liposomal Bupivacaine, a sustained-release formulation of Standard Bupivacaine, there has been renewed interest in regional intercostal nerve blockade.

Currently, most centers utilize some combination of epidural analgesia, systemic opioids, acetaminophen, nonsteroidal anti-inflammatory drugs, and gabapentin [18]. While this approach has proven effective, systemic opioids and epidural analgesia have many limitations. In the hospital, over 15% of patients receiving oxycodone will experience

altered mental status, nausea, or constipation [19]. In addition, it is essential to investigate other pain control strategies in consideration of the ongoing opioid abuse epidemic [20]. In regard to epidural analgesia, its placement is operator dependent, is limited by subject habitus, cannot be used in subjects on antiplatelets or anticoagulants, requires frequent postoperative monitoring, is associated with postoperative hypotension and urinary retention, and can result in epidural hematomas and abscesses that can be life-threatening [21, 22].

Intercostal nerve blockage with Liposomal Bupivacaine is an alluring alternative analgesic strategy as it is a sustained-release formulation of Standard Bupivacaine. Standard Bupivacaine loses efficacy after 8 hours, but Liposomal Bupivacaine has the potential efficacy of 96 hours [3]. Liposomal Bupivacaine is FDA-approved for single-dose infiltration into the surgical site to produce postsurgical analgesia since 2015 and brachial plexus regional nerve block since 2018. Its use for other forms of regional nerve block (including intercostal nerve block) is considered off-label.

Liposomal Bupivacaine is being used for local wound infiltration and regional nerve blocks across the surgical subspecialties, including thoracic surgery. The actual volume and breakdown of use in thoracic surgery is unknown; nonetheless, over the half the audience at the Society of Thoracic Surgery Annual Conference in January 2018 indicated that they routinely used Liposomal Bupivacaine in their practice. However, there is a clear deficit in data for thoracic surgery. There have been only two observational studies within thoracic surgery [12, 13]. They compared Liposomal Bupivacaine to epidural analgesia and found equivalence between the techniques. The results from these studies are subject to systematic error with selection bias and confounding. In addition, as the proportion of minimally invasive to open surgery has increased with the use of robotic-assisted thoracic surgery [23], many centers have eliminated epidural analgesia for the aforementioned reasons and the more pertinent question is Liposomal Bupivacaine versus Standard Bupivacaine.

As discussed in Section 1.2, there are ongoing trials that will provide less biased evidence in thoracic surgery assessing both local wound infiltration and intercostal nerve block with Liposomal Bupivacaine. The Minimally Invasive Thoracic Surgery Intercostal Nerve Block Study is unique, because it will assess intercostal nerve block and wound infiltration with Standard Bupivacaine and Liposomal Bupivacaine in both video-assisted and robotic-assisted lung resection.

A final consideration is the economic impact of Liposomal Bupivacaine. The direct costs of Liposomal Bupivacaine are 100 times the costs of Standard Bupivacaine, and at UCSF, the direct costs of Liposomal Bupivacaine are \$340 [24]. If Liposomal Bupivacaine is found to be efficacious, there could be cost savings through a reduction in use of other pain medications and postoperative complications. Alternatively, if Liposomal Bupivacaine is not found to be efficacious, it will only add to the economic burden on the health care system.

2.1 Risk / Benefit Assessment

The risks associated with Liposomal Bupivacaine and Standard Bupivacaine are similar. The most common adverse events include nausea, emesis, and/or constipation and are

expected to occur in >10% of subjects. Less common adverse events include dizziness, altered mental status, and hypersensitivity reactions with urticaria and/or pruritis. Very rare, but serious adverse events include neurologic toxicity with seizures and apnea, cardiac toxicity with atrioventricular nodal conduction abnormalities and cardiac arrest, and hypersensitivity reaction with anaphylaxis. Serious adverse events can be preventable with appropriate education, dosing, and administration. Most serious adverse events are found to be dose-related due to improper intravascular injection, inappropriate dosing, or slow metabolic degradation in patients with hepatic dysfunction [6]. For more information regarding adverse events, see prescribing information [2].

To minimize risk and limit the occurrence of serious adverse events, subjects will not be eligible for the study if they have evidence of hepatic dysfunction. In the operating room, dosing of Standard Bupivacaine will be based upon subject weight (See Section 8.3.2). The medication will be administered with proper technique by drawing back before injection to ensure the tip of the needle is not located within the lumen of a blood vessel. On the hospital ward, continuous cardiac telemetry will be used on all subjects and nursing will assess the mental status of each subject per shift.

3 STUDY OBJECTIVES

3.1 Primary Objective

The primary objective is to assess the analgesic efficacy of intercostal nerve block and wound infiltration by Liposomal Bupivacaine versus Standard Bupivacaine in subjects undergoing minimally invasive lung resection by robotic or video-assisted thoracoscopic surgery.

3.2 Secondary Objectives

The secondary objective is to assess if analgesia from the aforementioned interventions improve perioperative outcomes with reduction in pulmonary complications, length of stay, and direct hospital costs as well as improvement in quality of life.

4 STUDY DESIGN

4.1 Study Overview

This is a single center, double-blind, randomized, active-comparator controlled clinical trial. 80 subjects undergoing minimally invasive lung resection will be randomly assigned to one of two study groups: a one-time intraoperative intercostal nerve block and wound infiltration by Standard Bupivacaine or by Liposomal Bupivacaine. Each subject will receive standardized postoperative pain management. Evaluations will be taken at three-time points - preoperative clinic visit, index hospitalization following surgery, and postoperative clinic visit. Screening data will be reviewed to determine subject eligibility. Subjects who meet all inclusion criteria and none of the exclusion criteria will be entered into the study. Total duration of subject participation will be 30 days. Total duration of the study is expected to be 8 months. The treatment regimens are outlined below.

Study Treatment - Liposomal Bupivacaine

- 5cc of prepared drug will be percutaneously injected into each intercostal space 3-10 with a 22-gauge spinal needle under direct intrathoracic vision and subcutaneously into each wound at the conclusion of the surgery.

Active Comparator - Standard Bupivacaine

- 5cc of prepared drug will be percutaneously injected into each intercostal space 3-10 with a 22-gauge spinal needle under direct intrathoracic vision and subcutaneously into each wound at the conclusion of the surgery.

5 CRITERIA FOR EVALUATION

5.1 Primary Efficacy Endpoint

- Cumulative Daily In-Hospital Use of Opioids measured in mg of Oral Morphine Equivalents

The subjective sensation of pain is challenging to measure. Cumulative daily in-hospital opioid use measured in mg of oral morphine equivalents acts as a surrogate endpoint of pain and is commonly used in the literature. It provides objective data that are recorded on every subject in the medication administration record.

5.2 Secondary Efficacy Endpoints

- Cumulative Daily In-Hospital Pain Score: 0 (no pain) – 10 (most pain)

Pain Scores are a measure of the subject's postoperative pain that are recorded every four hours by the nursing staff. They are limited by the subject's perception of pain, concomitant pain medication use, and correlation with an abstract scaling system.

- Mean Time to First Opioid Use (hours)

Time to first opioid use is a surrogate marker of postoperative pain. It is limited by variations in anesthesiologist intraoperative analgesia techniques.

- Mean Time to Ambulation (hours)

Time to ambulation is a downstream marker of postoperative pain control. Ambulation is limited by subject motivation and/or physical disability.

- Pulmonary Complications: Pneumonia and Atelectasis requiring Bronchoscopy (y/n)

Pulmonary complications are a downstream marker of postoperative pain control as subjects with chest wall postoperative pain commonly splint with respiration. Splinting is associated with atelectasis and pneumonia.

- Liposomal Bupivacaine and Stand Bupivacaine Adverse Events (y/n):

- Gastrointestinal- nausea, emesis, constipation
- Hypersensitivity- pruritis, urticaria, anaphylaxis
- Cardiac- atrioventricular heart block, cardiac arrest

- Neurologic- dizziness, altered mental status, seizure
- Miscellaneous

To assess if there are differences in the complications between the study groups.

- Length of Stay (days)

Length of stay in the hospital can be used as downstream marker of overall postoperative course. It is limited by attending practice patterns.

- Total Opioid Prescription at Discharge (morphine equivalents in mg)

To assess if there are differences in the amount of opioid prescribed at discharge.

- Total Opioid Use as Outpatient (morphine equivalents in mg)

To assess if there are differences in the amount of opioid used after discharge.

- Direct Costs of Hospital Encounter (dollars)

The interventions in the study add costs over standard of care. It is important to evaluate the burden on the health care system in addition to subject outcomes.

- Quality of Life: Short-Form-8 Health Survey (Rand Health)

A change in quality of life before and after surgery will be assessed. This survey is limited by subject adherence to completion.

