7 CONCURRENT MEDICATIONS

Intraoperative analgesia provided by the anesthesia team will not be altered and will be performed per standard care. All subjects will be started on the same postoperative pain medications in the hospital and when discharged as outlined in Section 7.1.

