9.1 Clinical Assessments

9.1.1 Concomitant Medications

All concomitant medication will be documented at the preoperative and postoperative clinic visits. Dose, route, unit frequency of administration, and indication for administration and dates of medication will be captured.

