15.3 Analysis of Primary Endpoint

Null Hypothesis: There is no difference in cumulative in-hospital use of opioids in subjects who receive intercostal nerve block and wound infiltration Liposomal Bupivacaine or Standard Bupivacaine during minimally invasive lung resection.

Student's t-test will be used to assess the means of the cumulative total of in-hospital oral morphine equivalents. It is presumed that the data will be normally distributed. If this assumption is not met, transformation or nonparametric tests (Mann-Whitney U test) will be used. Moreover, as there are only 40 subjects per group, it is possible that we do not achieve effective randomization. If this occurs, we will utilize linear regression adjusting for age, sex, race, comorbidity, diagnosis, and procedure performed. A power of 0.8 and 2-sided alpha error set at 0.05 will be used to assess for statistical significance.

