15.6 Sample Size and Randomization

80 Subjects will be randomized to 1:1 to Liposomal Bupivacaine or Standard Bupivacaine by varying block size (4-8). 80 subjects will provide 80% power to detect a statistically significant effect with 2-sided alpha error set at 0.05 if the measured effect is 19% absolute reduction in cumulative daily in-hospital use of opioids.

The mean daily in-hospital usage of opioids is 35mg morphine equivalents with standard deviation of 12mg. This was estimated by review of previously published studies and corroboration with UCSF clinical practice patterns [12]. A 19% absolute reduction in cumulative daily in-hospital use of opioids corresponds to 1 fewer oxycodone dose per day, which was considered the minimum clinically significant effect.

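### The plan names intraoperative analgesia as a limit on time to first opioid use and keeps non-daily preoperative opioid users eligible, but no analysis adjusts for either: a modest loss of efficiency, not a bias.

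*Combined protocol and SAP*

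**What the plan says.** **Sources of variation.** Section 5.2 states a limitation of time to first opioid use: "It is limited by variations in anesthesiologist intraoperative analgesia techniques". Section 7 leaves that source of variation in place: "Intraoperative analgesia provided by the anesthesia team will not be altered and will be performed per standard care". Exclusion 7 in Section 6.3 removes daily preoperative opioid users only, so intermittent users can be enrolled.

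**Data capture.** Section 9.1.1 provides that "All concomitant medication will be documented at the preoperative and postoperative clinic visits", with dose and frequency, so preoperative opioid use is available at Visit 1. Sections 10.2 and Appendix 1 list concomitant medication at the surgery visit without detail.

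**Analysis.** The primary test in Section 15.3 is an unadjusted Student's t-test, with transformation or Mann-Whitney as the fallback. Regression is conditional on a judgement that randomization did not work ("as there are only 40 subjects per group, it is possible that we do not achieve effective randomization"); in that case "we will utilize linear regression adjusting for age, sex, race, comorbidity, diagnosis, and procedure performed". Section 15.4 names t-test, chi-squared and Kaplan-Meier, with no adjusted model. Neither opioid variable is in these analyses or in the baseline list of Section 15.2. Section 15.6 describes blocked randomization and mentions no stratification.

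**The concern.** The plan identifies a source of variation in an opioid endpoint, chooses not to standardize it, and then does not use it in the analysis. The one regression it foresees adjusts for six variables, none of which measures opioid exposure.

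Both variables could plausibly predict how soon a subject needs a first postoperative dose and how much opioid is used. If they do, leaving them out of the primary analysis keeps their contribution in the residual variance and widens the confidence interval. This matters more here because power on the plan's own inputs is below the stated 80%. That shortfall is a separate point; it is used below only as the starting value.

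**Working it through.** **Inputs from Sections 15.3 and 15.6.** 40 per arm; two-sided alpha 0.05; control mean 35 mg; SD 12 mg; the effect is stated as "if the measured effect is 19% absolute reduction in cumulative daily in-hospital use of opioids". I read 19% as relative to the mean: 0.19 × 35 = 6.65 mg. The calculation is on the daily scale that Section 15.6 uses.

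**Step 1: the plan's own figure.** Section 15.6 claims "80 subjects will provide 80% power to detect a statistically significant effect with 2-sided alpha error set at 0.05". Unadjusted, SE = 12 × √(2/40) = 2.68 mg, and 6.65 / 2.68 = 2.48. The noncentral t with 78 df gives 68.7% power (normal approximation 69.8%). The stated 80% is not reproduced.

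**Step 2: adjustment with its cost charged.** Let R² be the share of outcome variance explained by k covariates.
- Residual SD = 12 × √(1 − R²).
- SE = residual SD × √(2/40 × (N − 3)/(N − k − 3)), with N = 80. For k = 2 the factor for expected chance imbalance is 77/75.
- df = 80 − 2 − k, so 76 for k = 2.

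The documents give no covariate-outcome correlation, so R² is an assumption, shown as a range.

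| R² (assumed) | Residual SD, mg | SE, k = 2, mg | Power, k = 2 |
|---|---|---|---|
| unadjusted | 12.0 | 2.68 | 68.7% |
| 0 | 12.0 | 2.72 | 67.5% |
| 0.03 | 11.8 | 2.68 | 68.9% |
| 0.05 | 11.7 | 2.65 | 69.8% |
| 0.10 | 11.4 | 2.58 | 72.1% |
| 0.20 | 10.7 | 2.43 | 77.0% |
| 0.25 | 10.4 | 2.35 | 79.6% |
| 0.30 | 10.0 | 2.27 | 82.3% |

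Break-even against the unadjusted test is at R² of about 0.03. If R² is zero, the loss is 68.7 − 67.5 = 1.2 points.

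**Step 3: preoperative use alone.** For a yes/no covariate with prevalence p and a difference of d mg, R² = p(1 − p)d²/144. Assume p of 5% to 20% and d of 5 to 10 mg.
- Low end: 0.05 × 0.95 × 25/144 = 0.008.
- High end: 0.20 × 0.80 × 100/144 = 0.11.

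With k = 1 (77 df, factor 77/76), power is 68.1% at R² = 0, about 70% at 0.05 and about 73% at 0.11. Break-even is a little above 0.01. Taken alone, this covariate moves power by between about −0.6 and +4 to 5 points.

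**Step 4: is pre-block opioid dose a sound covariate?** Section 8.4.3 places the injection at the end of surgery, so the study drug cannot affect opioid given earlier. Three gaps remain.
- Section 8.1 determines assignment when the subject reaches the operating room, so the dose is pre-block but post-assignment. Section 8.2 lists patients, study staff and investigators as blinded, and does not name the anesthesia team.
- Section 5.1 sets no time window. If intraoperative opioid counts as in-hospital use, the covariate would be part of the outcome.
- No section says that opioid dose up to the injection is captured.

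**The case against.** The strongest reply is that an unadjusted t-test is valid after randomization, that both variables balance in expectation, and that adjusting for efficiency is a choice. That stands: a reader might infer bias from the wording in Section 5.2, but nothing in the documents supports it.

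A reader might also infer that precision is being given away free. The documents do not support that either. They give no correlation, two covariates cost about 1 point of power when they predict nothing, and Section 6.3 already excludes daily opioid users and patients treated for neuropathic pain, so the likely strong predictors are gone. With 5 mg more use in 5% to 10% of subjects, the preoperative indicator explains about 1% to 2% of variance, close to break-even for one covariate.

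Two further limits stand. Section 5.2 states its limitation for time to first opioid use only, whereas the power figures are for the primary endpoint. And the variance argument does not carry over to a Cox model, which has no residual variance to shrink and reports a conditional hazard ratio, while the plan's endpoint is mean hours. No precision gain is claimed there.

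Section 15 foresees a detailed SAP before the final analysis, which could add covariates. This answers only part of the point: whether the pre-block dose is collected has to be settled during conduct, and covariates are best chosen before outcomes are seen.

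**Conclusion.** The point holds as a modest matter of efficiency. The plan acknowledges variation in intraoperative analgesia, admits non-daily opioid users, and uses neither in any analysis. With two covariates charged, power would move from 68.7% to between 69.8% and 82.3% for R² from 0.05 to 0.30, and to 67.5% if they explain nothing. These figures rest on the 6.65 mg reading of the effect, the stated SD, full data on 40 per arm, and an R² that the documents do not supply.

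A reader might conclude that adjustment would restore the stated 80%. That would need R² a little above 0.25, which nothing in the documents supports, so adjustment is no substitute for reconciling the sample-size statement. A reader might also take the pre-block dose as already recorded and safe to use. Capture is explicit for preoperative medication only; the intraoperative dose is usable only under conditions. Nor does the argument extend to every opioid endpoint: Section 7.1 standardizes the discharge oxycodone at 20 pills, which leaves little variance to explain.

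**What to change.** 1. **Section 15.3:** pre-specify, regardless of observed imbalance, a linear model for the primary endpoint with treatment and any preoperative opioid use at Visit 1 (yes/no). State how it relates to the transformation and Mann-Whitney fallback, since a rank test takes no covariates, and to the contingent six-variable regression.
2. **Second covariate, conditional:** add opioid dose up to the block injection, in oral morphine equivalents, only if (a) Section 5.1 defines the endpoint window as postoperative, (b) the dose is a named eCRF field, and (c) Section 8.2 confirms that the anesthesia team is blind to assignment. Doses given after the injection stay out of the covariate.
3. **Section 15.4:** a Cox model with the same covariates may supplement the Kaplan-Meier estimate for time to first opioid use, with a statement that it reports a hazard ratio rather than mean hours.

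**Cost:** one added data field per subject for the pre-block dose; the yes/no item comes from the Visit 1 medication record. Up to two degrees of freedom, and about 1 point of power if the covariates prove uninformative. No added visits or subjects.
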